### **Statistical Analysis Plan**

Result analysis The investigators compare the differences between at baseline, at 3 month, and at 6 month. Statistical analyses will be performed using SPSS ver.18.0 (SPSS Inc., Chicago, IL, USA). Kolmogorov-Smirnov test was applied to test for normality of sample group data. The repeated measures analysis of variance with Bonferroni correction was used to analyze continuous outcome measures, including BCVA, CRT, total number of MAs, MA formation rate, MA disappearance rate, MA turnover, and perifoveal non-perfused area, before and after completion of 6 months of IVR therapy. A P-value <0.05 was considered statistically significant.

Table 1. Schedule of visits and procedures

Note: X = procedure to be performed, R = rescue treatment	Baseline Month 0 (Visit 1)	Month 1 (Visit 2)	Month 2 (Visit 3)	Month 3 (Visit 4)	Month 4 (Visit 5)	Month 5 (Visit 6)	Month 6 (Visit 7)
Informed consent	X						
Review eligibility criteria	X						
Demographics	X						
ETDRS BCVA	X	X	X	X	X	X	X
Slit lamp exam	X	X	X	X	X	X	X
IOP	X	X	X	X	X	X	X
OCT	X	X	X	X	X	X	X
Color Fundus Photo	X	X	X	X	X	X	X
FA	X			X			X
ICGA	X			X			X
Lucentis® injection	X	X	X	X	X	X	
Adverse events	X	X	X	X	X	X	X

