**(4) Study Design**

single center, prospective, interventional, one arm, pilot study

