**(5) Objectives**

**Objectives:** To evaluate the effects of intravitreal Ranibizumab injection on microvascular changes in eyes of mild-to-moderate NPDR with DME.

**Primary objective:** To compare microvascular changes assessed by microaneurysm counts in eyes of mild-to-moderate NPDR with DME after intravitreal Ranibizumab injection from baseline through 6 months after treatment.

**Secondary objectives:** To investigate other efficacy endpoints including other microvascular, anatomical, visual acuity change and safety in mild-to-moderate NPDR with DME after intravitreal Ranibizumab injection from baseline through 6 months after treatment.

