## **(7) Number of centers & patients, inclusion/exclusion criteria**

-25 patients, 1 center

- Inclusion criteria

- Patients (Male & female) > 40 years of age

- Type 2
- Best corrected visual acuity > 20/200 (Snellen equivalent using Early Treatment Diabetic Retinopathy Study chart)
- Central retinal thickness of > 300 um on optical coherence tomography
- Nonproliferative diabetic retinopathy (NPDR) with diabetic macular edema

- Exclusion criteria

- PDR – NVE & NVD
  - Early PDR – New vessels ; and criteria not met for high-risk PDR
  - High risk PDR – New vessels on or within one disc diameter of the optic disc (neovascularization of the disc) > standard photograph 10A with or without vitreous or preretinal hemorrhage ; or vitreous and/or preretinal hemorrhage accompanied by new vessels, either NVD < standard photograph 10A or new vessels elsewhere (NVE) > 1/4 disc area
- Vitreous hemorrhage
- Prior intraocular operation history.
  - Pars Plana Vitrectomy, RD surgery, recent (4 months) cataract Op, et al
- Prior any intravitreal injection history.
  - Lucentis, Eylea, Macugen, Avastin, Triamcinolone et al
- Prior pan retinal photocoagulation (PRP) or sector scatter photocoagulation was done.
- Uncontrolled hypertension.
- Uncontrolled glaucoma.

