**(11) Statistics**

We compare the differences between at baseline, at 3 month, and at 6 month. Statistical analyses will be performed using SPSS ver.12.0 (SPSS Inc., Chicago, IL, USA). The Wilcoxon signed rank test will be examined for timely changes in microvascular change (microaneurysm, non-perfusion area, cotton wool spot & hard exudate)

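### The analysis plan compares three visits under a Bonferroni correction of unstated scope and does not name month 6 minus baseline as the deciding contrast

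*Combined protocol and SAP*

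**What the plan says.** Section (5) frames the primary and secondary objectives as change "after intravitreal Ranibizumab injection from baseline through 6 months after treatment". The endpoints in section (10) use the same time frame.

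The Statistical Analysis Plan under section (10) states: "The investigators compare the differences between at baseline, at 3 month, and at 6 month". The method follows: "The repeated measures analysis of variance with Bonferroni correction was used to analyze continuous outcome measures". Seven outcomes are listed, and the sentence ends with "before and after completion of 6 months of IVR therapy". The threshold is given as "A P-value <0.05 was considered statistically significant". The plan does not state the number of comparisons corrected for, whether the correction runs over visits or outcomes, or which visit difference decides the result.

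Section (11) compares the same three time points by another method: "The Wilcoxon signed rank test will be examined for timely changes in microvascular change". It mentions no correction.

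The trial is described as "single center, prospective, interventional, one arm, pilot study" with "25 patients, 1 center". No power, planning effect or planning SD is given.

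**The concern.** Three time points give three pairwise differences: month 3 minus baseline, month 6 minus baseline, and month 6 minus month 3. If Bonferroni covers all three, the change over the full treatment period is held to a stricter threshold in order to pay for the other two. The month 6 versus month 3 comparison serves no stated objective. In a 25-patient study that can cost appreciable power and precision.

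The unstated family is a problem in its own right. The threshold for a 6-month claim could be 0.05, 0.025, 0.0167 or lower, depending on a choice that the plan leaves open until the data are in.

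The overall F test asks only whether the three means differ anywhere. Because the plan does not say what decides, a significant F could be taken for a 6-month effect when the change occurred at month 3 and had gone by month 6.

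**Working it through.** The documents state no power or sample-size calculation, so there is no figure of theirs to reproduce.

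**Inputs from the documents.** n = 25 (section 7); one arm, so the contrast is within-patient (section 4); significance level 0.05 and three time points (Statistical Analysis Plan).

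**Assumptions.** Two-sided tests, complete data, normally distributed changes, and a standardized change d = mean change / SD of change, which has to be assumed.

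**Threshold.** Three visit pairs: 0.05/3 = 0.0167. Two comparisons (each visit versus baseline): 0.05/2 = 0.025. Seven outcomes by three pairs: 0.05/21 = 0.0024.

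**Interval width.** The half-width is t × SD/√25 with 24 degrees of freedom. The t quantile is 2.064 at 0.05 and 2.574 at 0.0167. The ratio is 2.574/2.064 = 1.247, so intervals are 25% wider whatever the effect.

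**Power.** Paired t test, noncentral t with 24 degrees of freedom and noncentrality d√25 = 5d:

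| d (assumed) | 0.05 | 0.025 | 0.0167 | 0.0024 |
|---|---|---|---|---|
| 0.3 | 30% | 21% | 16% | 5% |
| 0.5 | 67% | 55% | 48% | 22% |
| 0.6 | 82% | 73% | 66.5% | 37% |
| 0.8 | 97% | 94% | 91% | 72% |
| 1.0 | 99.8% | 99% | 99% | 93% |

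The change detectable with 80% power rises from 0.58 to 0.69 SD. At 0.6 SD, 80% power needs 24 patients at 0.05 and 32 at 0.0167.

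**The only treated-eye change quoted.** Section (6) reports an earlier study's fall in microaneurysm number of 35.70% with SD 24.79%. Then d = 35.70/24.79 = 1.44, and power is about 100% at either 0.05 or 0.0167.

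**F test.** Simulated trials with 25 patients, three visits, correlation 0.5 and unit variance at each visit, so the change also has SD 1. With a 0.6 SD effect at month 3 and month 6 equal to baseline:
- The F test is significant in 86% of trials.
- The direct month 6 versus baseline test is significant in about 5% at 0.05 and about 1.7% at 0.0167.

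**Fixed sequence against three-pair Bonferroni, same simulation model.**
- Effect 0.6 SD at both visits: month 6 power is 82% with the sequence and 67% with Bonferroni; month 3 power is 71% and 67%.
- Effect 0.6 SD at month 3 and 0.3 SD at month 6: month 3 power is 29% with the sequence and 67% with Bonferroni.

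**The case against.** Bonferroni comparisons after a repeated measures ANOVA are valid and conservative, and this is a one-arm pilot with no power target. Several further points stand.

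- **The objective is not strictly one contrast.** A reader might infer that it asks only about month 6 versus baseline and that month 3 is surplus. The wording describes a period, both statistical sections name month 3, and angiography is scheduled at baseline, month 3 and month 6. Only month 6 versus month 3 lacks a purpose in the text.
- **The family of three is a reading.** The correction might cover two comparisons, only follow-up pairs after the F test, or outcomes. The closing words of the same sentence can even be taken as a plain before/after contrast.
- **No fixed loss can be attached to this trial.** A reader might infer that the correction costs about a fifth of the power. That holds when the uncorrected contrast has 80% power (80% falls to 64%, a relative loss of 20%), and 80% is not in the documents. The relative loss is 46% at 0.3 SD, 6% at 0.8 SD and about nil at 1.44 SD.
- **Section (11) may govern the microvascular outcomes.** Its Wilcoxon tests carry no stated correction, so the loss would not arise there.
- **The F-test harm depends on reporting.** Nothing in the plan directs that a significant F be presented as a 6-month result, and a corrected month 6 contrast would rarely be falsely significant.

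These points limit the size of the concern. They do not supply the missing contrast or the missing family. The 1.44 SD figure describes microaneurysms in another study and gives no assurance for visual acuity, macular thickness or non-perfused area. If section (11) governs, three visits are still compared with no deciding contrast and no control of error over visits.

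**Conclusion.** The point holds as a gap in specification with a conditional cost. The plan names no deciding contrast, leaves the Bonferroni family open, and treats the microvascular outcomes differently in two sections.

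The 25% widening follows if the family is the three visit pairs and corrected intervals are reported. The power loss needs that family plus an assumed effect: 19 points at 0.5 SD (67% to 48%), about 16 at 0.6 SD (82.1% to 66.5%), 6 at 0.8 SD, and almost none at 1.44 SD. With a family of two, the loss at 0.5 SD is 12 points (67% to 55%). All figures assume 25 complete patients and two-sided paired tests.

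The documents do not show that the plan as written loses a definite share of power, or that it would report a false 6-month effect. A cheap improvement in wording is warranted. It would not rescue a trial that is otherwise invalid.

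**What to change.** In the Statistical Analysis Plan, replace the ANOVA-with-Bonferroni rule with a fixed sequence for each outcome:

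1. Test month 6 minus baseline at two-sided 5%, with no correction for visits.
2. Test month 3 minus baseline at two-sided 5% only if step 1 is significant.
3. Report month 6 versus month 3 descriptively, with an estimate and interval.

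State that an overall F test, if kept, is not evidence of a 6-month effect. Apply the same sequence to the Wilcoxon tests in section (11), and reconcile the two sections so that each outcome has one method.

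The sequence holds visit-level error at 5% within each outcome. It does not control error across the seven outcomes, and the text should say so. Section (5) makes microaneurysm counts primary, while section (10) makes visual acuity and macular thickness primary. The sequence works under either, but the primary outcome has to be settled separately.

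The cost is wording only, with no added patients, visits or data. The price is that month 3 cannot be claimed unless month 6 is significant. If the effect fades, that matters: in the 0.6 SD to 0.3 SD example, month 3 power is 29% instead of 67%.

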**(9) Study duration**

**Until 30 Jul 2017(CSR submission)**

## **(10) Methodology**

Primary and secondary endpoints:

Primary endpoint:

To compare other visual acuity, anatomical changes after intravitreal Ranibizumab injection from baseline through 6 months after treatment.

i) The changes in best corrected visual acuity (BCVA) using ETDRS chart. ii) The central macular thickness - Circle Diameters : 1 mm ETDRS by spectralis OCT ; Heidelberg Engineering.

Secondary endpoints:

To compare microaneurysmal changes and perifoveal non-perfusion area and safety after intravitreal Ranibizumab injection from baseline through 6 months after treatment.

i) The total number of microaneurysm by fundus photo using Retmarker DR(version 1.0.2) software.

ii) The microaneurysm formation rate : Number of new MAs detected/month. iii) The microaneurysm disappearance rate : Number of MAs that resolved/month. iv)The microaneurysm turnover. v) Perifoveal non-perfusion area in FAG (mm^2) using ImageJ software (version 1.52a) by FAG image.

vi) Safety parameters : Systemic adverse events (MI, CVA, etc), Ocular adverse events (retinal detachment, RPE tear, endophthalmitis, uveitis, vitreous hemorrhage, subretinal hemorrhage, cataract , IOP elevation, etc).

single center, prospective, interventional, one arm, pilot study

Evaluation Participants will be evaluated with a full ocular examination at each visit (VA measurement, tonometry, slit lamp exam). Fluorescein angiography (FA) will be performed at baseline, at 3 months after baseline and at the last visit(6 months after baseline), and OCT will be performed monthly (baseline and 1, 2, 3, 4, 5, 6 months from baseline).

The MAs and perifoveal non-perfused areas in individual retinas were evaluated at 6 months using fundus photography and FA imaging. The Retmarker (version 1.0.2 by Retmarker Ltd, Coimbra, Portugal) software was used for automatic measurement and analysis of changes in number and extent of MAs on fundus photographs and to calculate the total number and turnover of MAs.

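### The planned repeated-measures ANOVA has no missing-visit rule or sphericity correction, so any patient who misses month 3 or month 6 is lost; a mixed model would retain them, with a stated degrees-of-freedom rule

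*Combined protocol and SAP*

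**What the plan says.** The study is described under (4) Study Design as "single center, prospective, interventional, one arm, pilot study", and section (7) sets the size as "25 patients, 1 center". No power, effect size or dropout allowance accompanies that number.

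The Statistical Analysis Plan states that "The investigators compare the differences between at baseline, at 3 month, and at 6 month" and that "The repeated measures analysis of variance with Bonferroni correction was used to analyze continuous outcome measures". It goes on to list seven of them by name: "including BCVA, CRT, total number of MAs, MA formation rate, MA disappearance rate, MA turnover, and perifoveal non-perfused area". The threshold is "A P-value <0.05 was considered statistically significant". It names no analysis set, no rule for missed visits and no sphericity test or correction. It does not say whether Bonferroni covers the visit pairs or the outcomes.

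On data collection, section (10) Methodology says "OCT will be performed monthly (baseline and 1, 2, 3, 4, 5, 6 months from baseline", and Table 1 also marks BCVA and colour fundus photographs at all seven visits. By contrast, "Fluorescein angiography (FA) will be performed at baseline, at 3 months after baseline and at the last visit(6 months after baseline". Section (11) Statistics names a different method, the Wilcoxon signed rank test, for microvascular changes including microaneurysms and non-perfusion area.

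**The concern.** Classical repeated-measures ANOVA works on complete rows. A patient who misses only month 3 still has a valid pair of baseline and month-6 values, but is removed. So is a patient who leaves after month 3, although the baseline and month-3 values are in hand. With 25 patients each removal costs precision. If those who leave are the ones who responded less, the completers overstate the benefit.

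The omnibus F test also assumes that the differences between visits have equal variances. An untreated baseline followed by two on-treatment visits is a setting where months 3 and 6 may well be more alike than either is to baseline. In that case the uncorrected test rejects too often.

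Both outcomes that the Methodology lists as primary, BCVA and central thickness, go through this analysis.

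**Working it through.** **Inputs from the documents.** N = 25 (section 7); three analysed visits, threshold 0.05 and seven outcomes (Statistical Analysis Plan). **Assumed, because the documents give nothing:** the missing rate m per follow-up visit, the correlations between visits, the dropout mechanism and the effect size. The plan gives no power or precision figure to reproduce.

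**1. Patients retained.** With visits missed independently, complete cases = 25(1 − m)².
- m = 0: 25
- m = 5%: 25 × 0.95² = 22.6
- m = 10%: 25 × 0.90² = 20.3
- m = 15%: 25 × 0.85² = 18.1
- m = 20%: 25 × 0.80² = 16.0

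**2. Precision of month 6 minus baseline.** Patients with both baseline and month 6 number 25(1 − m). Requiring month 3 as well cuts this to 25(1 − m)², which alone multiplies the variance by about 1/(1 − m): 1.11 at 10% and 1.25 at 20%. A likelihood analysis also draws on the month-3 values of patients without month 6, which widens the gap. With assumed correlations of 0.4 to 0.8, the complete-case variance is about 14 to 22% higher at 10% missing and 37 to 41% higher at 20%.

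**3. Bias when dropout depends on the month-3 change.** In simulation at n = 25, strong dependence (19.4 completers on average) gave −0.80 from completers and −0.58 from the mixed model, against a true −0.57. Other assumed mechanisms gave a completer bias of only 0.03 to 0.05 SD on a 0.7 SD fall. The direction is predictable; the size depends on a mechanism that the documents do not describe.

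**4. Sphericity.** With three visits, epsilon cannot fall below 0.5. The worst-case size of the uncorrected test at n = 25 is P(F(1, 24) > 3.19) = 8.7%, where 3.19 is the 5% critical value of F(2, 48). Simulated size with equal variances, for correlations between months 0–3, 0–6 and 3–6:
- 0.5/0.5/0.7: epsilon 0.91, size 5.6%
- 0.7/0.7/0.9: epsilon 0.75, size 6.3%
- 0.4/0.4/0.9: epsilon 0.63, size about 7.5%

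The Greenhouse-Geisser correction held 4.7 to 5.2% in these settings.

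**5. Level of the alternative.** The omnibus visit test from an unstructured mixed model, complete data, n = 25:
- Wald chi-square: 7.7%
- F with naive df (2, 24): 5.7%
- Kenward-Roger: 4.6 to 4.7% simulated, and 4.9 to 6.3% with 10% missing per visit (Monte Carlo SE about 0.7 points)

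The degrees-of-freedom rule therefore decides whether the level is kept.

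**6. Power.** Assumed standardised effect: (35.70 − 13.95)/38.21 = 0.57, from the background figures in section (6).
- Omnibus test at 0/10/20% missing: mixed model 71/68/67%; complete-case Greenhouse-Geisser ANOVA 81/70/56%.
- Month 6 minus baseline (separate simulation, assumed change of 0.57 SD): mixed model 69/70/63%; complete-case paired test 69/61/49%. With complete data the two are the same test.

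**7. Across outcomes.** Seven outcomes each at 0.05 give 1 − 0.95⁷ = 30.2% if independent. The choice between ANOVA and mixed model does not change this.

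**The case against.** The strongest reply is that this is a one-arm pilot with no stated missing-visit rate, so the loss may never occur. That stands: a reader might infer that the plan will discard patients, but the documents support only the conditional statement.

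A reader might also infer serious inflation of the type I error. It is capped at 8.7%, is near 5.6% under moderate correlations, and goes away with a single phrase adding a Greenhouse-Geisser correction. Bonferroni-adjusted paired contrasts with their own error terms do not need sphericity at all. This also stands, but neither remedy recovers the deleted patients.

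On power, the mixed model loses to Greenhouse-Geisser ANOVA for the omnibus test with complete data (71% against 81%). That is a real cost if the omnibus test is the target. It does not arise for month 6 minus baseline, where nothing is lost with complete data.

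Section (11) assigns Wilcoxon to the microvascular outcomes, and a pairwise test keeps a patient who misses only month 3 in the baseline-to-month-6 comparison. For those outcomes the loss may not occur, depending on which text governs. BCVA and central thickness are not affected by that conflict.

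Finally, leaving the other four monthly visits out of the comparison is a design choice stated consistently in both statistical sections. It is not an error.

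**Conclusion.** The point holds in conditional form. As written, the analysis is complete-case and carries no sphericity correction. At an assumed 5 to 15% missing per follow-up visit it would keep about 22.6 down to 18.1 of 25 patients. At 10 to 20% missing, the variance of the month-6 change would be about 14 to 41% above that of a likelihood analysis. Bias appears if dropout follows earlier response, but its size cannot be fixed from the documents. With full attendance, only the sphericity issue remains, bounded at 8.7%.

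A reader might infer that a mixed model secures the 5% level throughout. It does so approximately, per outcome, and only with a small-sample degrees-of-freedom rule; it does nothing for multiplicity across seven outcomes. Nor does it fit every listed outcome. Microaneurysm formation rate, disappearance rate and turnover are interval measures with no baseline value, so a change from baseline is undefined for them.

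The change is worth making before analysis because it needs no new data. The present wording is not fatal to the study.

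**What to change.** First reconcile the Statistical Analysis Plan with section (11) on ANOVA versus Wilcoxon for the microvascular outcomes, and name one method per outcome.

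Then, for BCVA and central thickness, and after that reconciliation for total microaneurysm count and non-perfused area, specify:
- a REML linear mixed model with visit as a categorical effect and an unstructured 3x3 covariance over months 0, 3 and 6;
- every patient with a baseline value included;
- Kenward-Roger degrees of freedom or, if the software lacks them, a conservative df equal to the number of patients with month 6, minus 1;
- month 6 minus baseline as the main contrast, with Bonferroni stated to apply to the visit contrasts;
- a sensitivity analysis to the missing-at-random assumption.

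Do not apply this contrast to formation rate, disappearance rate or turnover; give them their own analysis. A seven-visit model with a structured covariance is an optional sensitivity analysis for BCVA and OCT only, since an unstructured 7x7 matrix has 7 × 8/2 = 28 parameters. If the ANOVA is kept, add at least a Greenhouse-Geisser correction and a missing-visit rule.

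The cost is SAP wording and some programming, with no extra patients or visits. The drawbacks are reliance on missing at random (weaker than what complete-case analysis needs) and lower omnibus power when attendance is full.

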Kohner and Sleightholm^13 describe this concept at first time in 1986, its association with the number of microvascular flow and the severity of diabetic retinopathy. In recent years it is reported that measuring the number of microaneurysm and the turnover rate associated with the appearance or disappearance of microaneurysm, are predictors in progression of diabetic retinopathy and macular edema.

To delay the progression of diabetic retinopathy and to improve macular edema, the laser photocoagulation have been the important role. Although the laser photocoagulation have had treatment effect in the diabetic retinopathy by reducing the amount of VEGF in micraneurysm and by degenerating the neovascularization after laser therapy, there was a problem that has many limitations - peripheral visual field defects, night blindness, progression of macular edema etc., and that the disease does not cured in a good time because of limits of laser therapy due to cataract, vitreous hemorrhage and turbidity. As an alternative method to solve these limitations, there is an anti-VEGF therapy. According to a previous study result, intraocular injection of Bevacizumab inhibits occurring of neovascularization by blocking the VEGF receptor .

Recently, several studies have been reported that when injected intravitreal anti-VEGF, macular edema is improved and neovascularization is inhibited, by reducing the leakage of neovascularization.

Especially, Leicht SF et al reported the number of microaneurysms and turnover rate in NPDR(non-proliferative diabetic retinopathy) patients injected with Ranibizumab. And the result showed entire number of the microaneurysms and turnover rate are decreased, which could be mean the regression of diabetic retinopathy and it could decide the therapeutic effect.

On this study, through the fluorescein fundus angiography, the average number of microaneurysms was significantly decreased after intravitreal injection of anti-VEGF therapy ( $p < 0.05$ ). The decrease of  $35.70 \pm 24.79\%$  in the treatment group was statistically higher than  $13.95 \pm 38.21\%$  in the control group of the fellow eye ( $p < 0.05$ ).

The result is found because decreased concentration of intravitreal VEGF inhibits the progression of diabetic retinopathy, such as endothelial cell proliferation and endothelial cell damage on retinal capillary and perivascular cells.

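### Microaneurysm formation rate, disappearance rate and turnover have no pre-treatment value, so the planned before/after ANOVA cannot be run for them

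*Combined protocol and SAP*

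**What the plan says.** The Statistical Analysis Plan compares baseline, month 3 and month 6. It applies one method, a Bonferroni-corrected repeated-measures ANOVA, to seven continuous outcomes. BCVA, CRT and total MA count come first, followed by "MA formation rate, MA disappearance rate, MA turnover, and perifoveal non-perfused area, before and after completion of 6 months of IVR therapy".

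Section (10) Methodology defines two of these as rates: "The microaneurysm formation rate : Number of new MAs detected/month" and "The microaneurysm disappearance rate : Number of MAs that resolved/month". Turnover is named as an endpoint without a formula. The same section says the software is used for "analysis of changes in number and extent of MAs on fundus photographs and to calculate the total number and turnover of MAs". Section (6) Study rationale describes "the turnover rate associated with the appearance or disappearance of microaneurysm".

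The lead sentence for the secondary endpoints in section (10) is worded differently from the SAP: "To compare microaneurysmal changes and perifoveal non-perfusion area and safety after intravitreal Ranibizumab injection from baseline through 6 months after treatment".

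Table 1 begins at Month 0 and has no screening or run-in column. A colour fundus photograph is scheduled at every visit from Month 0 to Month 6. Injections are scheduled at Months 0 to 5, so the first photograph and the first injection fall on the same visit. The order within that visit is not stated.

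Section (4) describes a "single center, prospective, interventional, one arm, pilot study".

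**The concern.** An MA can be called new or resolved only against an earlier image of the same retina. A formation or disappearance rate therefore belongs to an interval between two dated photographs, not to a visit. A pre-treatment rate needs two photographs at or before the first injection, and the schedule supplies one at most.

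The SAP nevertheless treats these outcomes as if each had a value at baseline, like BCVA or a lesion count. The analyst would have to drop the level, choose intervals the plan does not name, or set the baseline rate to zero. The last option builds in a difference.

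With one arm, no untreated group can supply the missing rate. Section (6) presents a fall in MA number and turnover as a possible sign of regression of retinopathy. A fall in turnover reported as before versus after therapy would therefore be read as efficacy, although the data could only show a difference between two periods on treatment.

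**Working it through.** The plan gives no figure on this point to reproduce. The check is a count from Table 1 and the endpoint definitions.

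**Inputs**
- Photographs (Table 1): Months 0, 1, 2, 3, 4, 5, 6, which is 7.
- Injections (Table 1): Months 0, 1, 2, 3, 4, 5; the first is at Month 0.
- Analysis times (SAP): Months 0, 3, 6.
- Outcomes in the ANOVA (SAP): 7, of which 3 are interval measures.
- Patients (section (7)): 25.
- Assumption: the Month 0 photograph is taken before the Month 0 injection. If it is not, there is no pre-treatment photograph at all and the problem is larger.

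**Pre-treatment intervals**
- Photographs at or before the first injection: 1.
- Intervals that 1 photograph can form: 1 − 1 = 0.
- Monthly intervals wholly before treatment: 0 of 6.
- Intervals between analysis times (0-3 and 3-6) wholly before treatment: 0 of 2.
- Baseline values available for formation rate, disappearance rate and turnover: 0.

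**Effect on the planned comparisons**

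| | Single-image outcome (e.g. total MA count) | Interval outcome |
|---|---|---|
| Levels available | 3 (months 0, 3, 6) | 2 (0-3, 3-6), both on treatment |
| ANOVA df with 25 complete patients | 2 and 2 × 24 = 48 | 1 and 24 |
| Pairwise contrasts | 3 | 1 |
| Bonferroni level, if taken over the visit pairs | 0.05/3 = 0.0167 | 0.05/1 = 0.05 |

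With two levels, the repeated-measures ANOVA is the same as a paired t-test.

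If all three visit pairs are tested for each outcome, there are 7 × 3 = 21 contrasts. Two of the three pairs involve baseline, so 3 × 2 = 6 of the 21 do not exist. If turnover is set aside because its formula is missing, the counts are 2 of 7 outcomes and 2 × 2 = 4 of 21 contrasts. If only month 0 versus month 6 was meant, 3 of 7 contrasts do not exist (2 of 7 without turnover). The SAP states neither the list of contrasts nor the Bonferroni family.

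**Why the intervals must be named (illustration only)**

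Suppose the analyst used cumulative intervals, 0-3 and 0-6 months. Assume a constant formation rate λ and a constant closure hazard μ = ln 2 / half-life, with N MAs present at Month 0. Neither the model nor the half-lives are in the documents.
- New MAs seen per month over T months: λ(1 − e^(−μT))/(μT).
- Resolved MAs per month over T months: N(1 − e^(−μT))/T.
- For both, the 0-6 month rate divided by the 0-3 month rate is (1 + e^(−3μ))/2.

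| Assumed half-life (months) | Ratio | Apparent fall |
|---|---|---|
| 3 | 0.750 | 25% |
| 6 | 0.854 | 15% |
| 12 | 0.920 | 8% |
| 24 | 0.959 | 4% |

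These falls occur with no biological change. With equal intervals (3-6 versus 0-3 months) at steady state the ratio is 1.00.

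**The case against.** The strongest reply is that the SAP sentence is a loose list with a shared ending. On that reading, baseline is only the reference image, and the section (10) wording, from baseline through 6 months, is what was meant. That wording is computable, so the endpoints are not lost. It yields an on-treatment rate, however, not a baseline value of the rate. The SAP names all three outcomes individually under a three-visit comparison, and no other section gives them a different analysis.

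Section (11) Statistics is a second, conflicting analysis text. It specifies a Wilcoxon signed rank test and does not name the three rates. If it governs, its microaneurysm analysis might mean the count alone, which has a baseline. But it uses the same three time points and adds no earlier photograph, so it does not fill the gap. It does mean that a correction must cover both sections.

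Three further points stand in part:
- Treating turnover as an interval measure is an inference from sections (6) and (10). Formation and disappearance do not depend on it.
- The cumulative-interval figures illustrate the cost of undefined intervals. They do not measure the missing baseline.
- These are secondary endpoints in a 25-patient pilot, which limits the severity.

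**Conclusion.** The concern holds and should be fixed. For formation rate, disappearance rate and turnover, the baseline level of the planned ANOVA does not exist, and the plan does not say which interval each value covers. This affects 3 of 7 outcomes and, if all visit pairs are tested, 6 of 21 contrasts.

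The conclusion rests on Table 1 being the full image schedule and on no earlier clinic photographs being used; the documents mention none and do not require one for eligibility. For turnover it also rests on the inference that it is measured between images.

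The limits are clear. Section (10) lists the three measures as secondary. BCVA, CRT, total MA count and non-perfused area each have a baseline value. The three rates remain usable as on-treatment descriptions.

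**What to change.** For these three outcomes only:

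1. Remove the baseline level and the before/after wording from the SAP, and make section (11) agree.
2. Give the turnover formula, and state which two photographs each value uses.
3. Compute each measure over equal, non-overlapping intervals: months 0-3 and 3-6. These match the SAP time points and use scheduled photographs, but leave the month 1, 2, 4 and 5 photographs unused. If the sponsor prefers monthly intervals, average the three monthly rates within each period and say so.
4. Report the result as early versus late on treatment, either descriptively or with one paired comparison. Choose one in the SAP, and claim no change from before treatment.
5. Rest the before/after microaneurysm question on total MA count.

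If the sponsor wants a pre-treatment rate from earlier clinic photographs, the SAP must say so and define the allowed window. The exclusion "Prior any intravitreal injection history" means such an interval would be free of injections. It would not necessarily be free of all treatment, because the laser exclusions name only panretinal and sector scatter photocoagulation.

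The cost is wording: no new visits or images. The price is that no before/after claim can be made for the three measures, and the comparison of total MA count remains uncontrolled in a one-arm trial. Parts of section (10) and the SAP are in the past tense, and section (10) cites a software date (23/04/2018) later than the study end date in section (9) (30 Jul 2017). If the data have already been examined, the change should be labelled post hoc.
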